#### 10.4.3 ANALYSIS OF THE SECONDARY ENDPOINT(S)

The secondary endpoint will be analyzed and presented in the same manner as the primary endpoint, with the same model assumptions and the same approach to missing data. The analysis will not depend on findings or analysis of the primary endpoint.

The secondary endpoint, like the primary endpoints, is a continuous score.

---

#### 10.4.4 SAFETY ANALYSES

N/A

---

#### 10.4.5 BASELINE DESCRIPTIVE STATISTICS

We will compare study arms descriptively across baseline levels of endpoints, age, gender, and race without inferential analysis.

---

#### 10.4.6 PLANNED INTERIM ANALYSES

We will conduct an interim analysis of the primary endpoints to provide data for a SBIR Phase II application, likely six months into the study period. The analysis, while lower-powered, will be the same analysis as described in 2.4.2 above. The interim analysis will not prompt study discontinuation or participant withdrawal by the investigators. Type I error will be addressed in the final analysis as described in 2.4.2.

#### 10.4.7 SUB-GROUP ANALYSES

We do not plan any sub-group analyses; the study is not powered for stratified analyses.

#### 10.4.8 TABULATION OF INDIVIDUAL PARTICIPANT DATA

We will not tabulate individual participant data.

#### 10.4.9 EXPLORATORY ANALYSES

We will conduct an exploratory analysis of association between study adherence (level of use, by number of sessions, cumulative length of time of use of GogyUp Reader) and primary endpoint.

### 11 SUPPORTING DOCUMENTATION AND OPERATIONAL CONSIDERATIONS

#### 11.1 REGULATORY, ETHICAL, AND STUDY OVERSIGHT CONSIDERATIONS

##### 11.1.1 INFORMED CONSENT PROCESS

The COVID-19 pandemic presents unique challenges to patient and staff safety. Diabetic patients in particular are more susceptible to infection. Potential partner clinics have expressed concern of hosting additional personnel during the recruitment, consent, and enrollment phases. The team has therefore decided to conduct consent through the e-consent procedures described below. A benefit to this approach is the opportunity to leverage assistive technology and communication tools to tailor the recruitment / consent / enrollment process to different candidate preferences and needs for reviewing information and interacting with the research coordinator.

##### 11.1.2 CONSENT/ASSENT AND OTHER INFORMATIONAL DOCUMENTS PROVIDED TO PARTICIPANTS

To ensure each candidate is fully informed about the study expectations and risks, candidates may select from a menu of options that provide various modes of communication to accommodate individual candidate's preferences and allow the greatest amount of access to consent information, support for understanding and opportunities to demonstrate their understanding – at scale.

Prior to enrollment, each candidate will meet with the research coordinator through either a teleconference or a video conference to confirm each candidate is fully informed about

# RCT of Assistive-Reading Technology for Post-Visit Type 2 Diabetes Patient Education

Version 1.4

Protocol 1

10 February 2023

the purpose, risk, and expectations for involvement in the study. At multiple stages, a comprehensive study disclosure document detailing the study intervention, study procedures, and risks will be available to the participant. Signed informed consent will be completed prior to starting the study intervention.

To accommodate individual candidate preference, English proficiency, as well as varying technology literacy and print literacy skillsets, candidates will be able to choose from several options to receive disclosure information, engage with the study's research coordinators, and proceed through the recruitment / consent / enrollment process.

Regardless of the candidate's chosen option, the process will progress through these steps:

- 1) Outreach Letter via postal mail. (Recruitment)
- 2) Provide Contact Information via HIPAA compliant intake form.
- 3) Review Disclosure Information
- 4) Confirm Consent
- 5) Enrollment & Assignment
- 6) Baseline Assessment
- 7) Participant Provisioning
- 8) Follow-Up Assessment
- 9) Thank You

All recruitment and consent materials are submitted with this protocol under section 15 and are presented through one or more systems listed in the table below.

11.1.3 HIPAA COMPLIANT SYSTEMS EMPLOYED FOR INFORMED CONSENT AND ENROLLMENT PROCESS

System	Function	HIPAA Compliance
JotForm	Candidate Intake Disclosure Information Signature: Informed Consent Baseline Assessment Follow-Up Assessment Candidate / Participant Database Appointment Scheduling	https://www.jotform.com/hipaa/
Google Workspace Business	HIPAA compliant e-mail HIPAA compliant telephone and SMS (Google Voice) Device management (for tablets requested by participants without intent access or computing device).	HIPAA Business Associate Agreement Covered Services
Zoom	Video Conferencing for interviews and any ad hoc information requests candidates / participants might have.	HIPAA Business Associate Agreement

Figure 1, Study Participant Workflow, illustrates how the candidate's engagement options and study disclosure and consent materials are interconnected and presented to potential study participants.

# RCT of Assistive-Reading Technology for Post-Visit Type 2 Diabetes Patient Education

Version 1.4

Protocol 1

[figure not shown]
[figure not shown]
10 February 2023

## 11.1.4 RECRUITMENT / CONSENT / ENROLLMENT / PLACEMENT & FOLLOW UP WORKFLOW AND DOCUMENTATION

[figure not shown]
[figure not shown]
[figure not shown]
[figure not shown]
[figure not shown]
[figure not shown]
[figure not shown]
### Partnering Health System

- Generates list of 2,000+ candidates.
- Mails letter to candidate pool.

#### Candidate Recruitment Letter

- Mark participant inactive.
- Enroll new candidate.
- Mark inactive participant as "Discontinued"

Step	Description	Documents & Scripts
1	
Recruitment Letter
 
Research staff at M Health Fairview, the health system we are partnering with for recruitment, will pre-screen and develop a list of 2,000+ qualified study candidates based on the inclusion and exclusion criteria described previously.
 
M Health Fairview mails the Candidate Recruitment Letter to those candidates.
 
The letter contains top level information about the study and presents several ways to learn about the study and contact GogyUp's research coordinator through SMS text, voice call, email, or scanning a QR code to visit the landing page for the study on gogyup.com (step 2a.1).
	Candidate Recruitment Letter
2a.1	
Candidate Recruitment Landing Page: gogyup.com/study
 
To prevent individuals not in the candidate pool from engaging with the study, the study's recruitment landing page is only accessible through the QR code on the Recruitment Letter, the URL listed in the recruitment letter, or if individually provided to candidates / participants through scripted communications. The page is also hidden from search engines, the gogyup.com homepage and gogyup.com site index.
	Study Landing Page: gogyup.com/study
2a.2	
Candidates may access disclosure information about the study and GogyUp Reader prior to choosing to contact the research coordinator through email, phone, or SMS texting or opting to continue on to Step 2a.2 - the intake form.
 
The Candidate Intake form captures basic contact information and provides three options to review disclosure information, described further below in these sections:
 
 
• Online review of disclosure information online and pre-screen their level of understanding for each section (Option 3a).
 
• Receive the disclosure information as a PDF attachment via e-mail (Option 3b).
 
• Request that the research coordinator initiate a phone call with the candidate (Option 3c).
 
• Schedule an intake call via a Zoom videoconference or phone conference with the research coordinator (Option 3d).
 
	Candidate Intake Form Online Disclosure Information & Candidate Pre-Screen Form

Step	Description	Documents & Scripts
2b to 2d	
Initial Candidate Contact
 
If candidates choose to contact the research coordinator directly, these scripts serve to standardize the conversation and ensure equitable and equal access to information:
 
 
• Inbound SMS text response and Outbound follow-up response if no reply
 
• Inbound voice call script
 
• Outbound voice call to candidate and follow-up script           
 
◦ Outbound voicemail message (no answer / no reply follow-up)
 
 
 
• Inbound eMail response script (automated)
 
• Outbound eMail response follow-up if no reply (automated)           
 
◦ both email messages will contain links to the Online Disclosure Document and Consent Form
 
 
 
 
All communication with an individual candidate and participant is captured in a HIPAA-compliant JotForm database record for that individual.
	
Study Landing Page:  gogyup.com/study
 
Scripts:
 
 
• SMS Response
 
• SMS Follow-Up
 
• Incoming Call
 
• Voicemail Greeting
 
• Outbound Follow-Up
 
• Voicemail Follow-Up – 1st Message
 
• Voicemail Follow-Up – 2nd Message / No Response
 
• Outbound eMail Response (automated)
 
• Outbound eMail – No Response (automated)
 

Step	Description	Documents & Scripts
3a	
Study Disclosure Document and Pre-Screening Form
 
The Study Disclosure Document and Pre-Screening Form is modeled off of Pearl Pathways' consent documentation: the All-in-One Consent Form and the Federally Required Elements for Consent.
 
Disclosure information is arranged thematically. To ensure equitable access to information, each content section contains a verbatim audio recording of the text content. Following each section is a screening question that asks the candidate to indicate whether they understand the information covered in each disclosure document section or if the candidate needs additional information:
 
Prompt: Do you understand [ topic ]?
 
A) Yes.
 
B) I have a question.
 
C) I want this explained to me
 
We will assume that candidates answering with choice C may be indicating they do not understand the information and the research coordinator should be prepared to explain the topic during the consent interview.
 
Each section also lists the contact information for the research coordinator (text messaging / phone / email) should the candidate want to stop and ask questions directly.
 
Please note: the screening questions are not designed to exclude candidates from the study. Rather, their purpose is to provide the research coordinator with advance knowledge of each candidate's depth of understanding in order to facilitate an efficient and productive consent interview (step 4).
	Online Study Disclosure Document & Pre-Screening Form
3b	
Review Consent via Email
 
The Study Disclosure Document and Screening Form will be sent as a password-protected, PDF attachment to the candidate's email address in 2a – d. Each attachment will have a unique identifier and will be pre-filled with the candidate's contact information. If candidate chooses to respond to prompts within the PDF, the candidate's study database record will be updated with the candidate's responses.
 
eMail text contains:
 
 
• contact information for research coordinator
 
• option to schedule an intake call for 1:1 consent review
 
• option to complete consent review online
 
 
Password to access the document will be texted or shared in a follow-up call with the candidate.
	
Study Disclosure Document (PDF)
 
Script:
 
 
• eMail – Outgoing
 
• eMail – Disclosure Review
 

# RCT of Assistive-Reading Technology for Post-Visit Type 2 Diabetes Patient Education

Version 1.4

Protocol 1

10 February 2023

Step	Description	Documents & Scripts
3c	
Research Coordinator Calls Candidate
 
Candidate chooses this option by indicating their preference on the intake form accessed through gogyup.com/study.
 
Research Coordinator (RC) is notified via automation from JotForm and schedules the call, when possible, according to preferred time windows the candidate indicated on the intake form.
 
During the call, the RC will review and complete the Online Disclosure Document and Prescreening Form (Option 3a) with the Candidate. The candidate will receive a copy of the disclosure document and form responses via email which will also be automatically added to the candidate's database record.
 
If the candidate chooses to proceed, the call may continue to Step 4, 5, 6, and 7 with the option to switch to an online video session through Zoom.
	
Online Study Disclosure Document & Prescreening Form
 
Script:
 
 
• Step 3c: Intake Interview Script
 

3d	
Schedule Intake Call with Research Coordinator
 
Candidate chooses this option by selecting the Intake Call option on the intake form, choosing an open timeslot in the JotForm form and whether the call should be a tele- or videoconference.
 
As with Step 3c, the research coordinator will review the Online Disclosure Document and Pre-Screening Form with the Candidate in real time and the candidate will receive a copy of the form via email to review prior to the Consent Confirmation step.
 
If the candidate chooses to proceed, the call may continue to Step 4, 5, 6, and 7 with the option to switch to an online video session through Zoom.
	
Online Study Disclosure Document & Pre-Screening Form
 
Jotform Intake page
 
Scripts:
 
 
eMail opt-in confirmation
 
eMail opt-in
 

4	
Consent Interview & Signatures
 
After the candidate has had the option to review the study disclosure information, this step is to provide consent authorization.
 
This step is broken into three sub-steps:
 
4a: Schedule Interview
 
4b: Consent Interview
 
4c: Consent Signature
 
Depending on their choices through the workflow, candidates may not experience all three.
	Online Consent Form
4a	
Schedule Interview
 
Ideally, this step is needed only if the candidate does not have the time (10 to 15 minutes) to review the study disclosure information with the researcher coordinator. This option is designed to efficiently schedule a follow-up session with the candidate.
	
JotForm Consent Interview page
 
Scripts:
 
 
eMail: opt-in confirmation
 
eMail: opt-in reminder email
 

Step	Description	Documents & Scripts
4b	
Consent Interview
 
This interview is a scheduled online / over-the-phone session between the research coordinator, the candidate.
 
Once the candidate joins the phone or online conference, the coordinator:
 
 
1. Reviews with the candidate's unanswered questions noted on the online disclosure document and consent form.
 
2. Asks open-ended questions to assess the depth of the candidate's comprehension of the study and the activity the candidate is consenting to.
 
 
If the coordinator confirms the candidate has demonstrated understanding, the candidate is invited to sign the consent form (step 4c).
 
Note: the script outlines two sub-procedures if the candidate does not demonstrate sufficient depth of comprehension:
 
 
1 If the candidate states they are unable to read the information in the Online Disclosure Document or responses indicates their level of literacy or English proficiency would prevent understanding, a witness will be added.
 
2 To ensure the most inclusive study population, candidates have the option to reschedule if they need more time and interaction with the coordinator to understand the research and the risks and benefits involved.
 
	
Online Study Disclosure Information and Prescreening Form
 
Script: Step 4b - Consent Confirmation Interview

4c	
Consent Signature
 
To gather the candidate's consent signature, the research coordinator launches a video conference in ZOOM, an accessible and HIPAA-compliant video / audio conferencing and screen sharing program and shares the conference link as well as a link to the online JotForm form to be signed.
	
Script: Step 4c – Consent Signature
 
Online Consent Form

5	
Enrollment & Assignment
 
The research coordinator verifies the participant's contact information and mailing address where the participant may securely receive packages.
 
The research coordinator then refers to the allocation sequence to determine intervention or comparison arm for the newly recruited participant.
 
Depending on the result, the participant is placed in the control or GogyUp Reader group.
 
If the participant is out of time, the RC schedules a baseline assessment with the participant prior to officially enrolling the participant.
	
Script: Step 5 - Enrollment & Assignment
 
Randomization Allocation Sequence

Step	Description	Documents & Scripts				
6	
Baseline Assessment & Onboarding
 
Research coordinator (RC) conducts the baseline assessment (remotely and preferably through Zoom video conference) of the Health Literacy Questionnaire (HLQ) with additional demographic questions for patient age in years, gender, self-identified race and ethnicity, and duration of diabetes diagnosis.
 
Before the participant signs-off, the RC will schedule and/or confirm the Follow-Up assessment, ideally scheduled close to any follow-up appointment the participant has scheduled with their provider.
 
The script for this step includes procedures for if the participant misses the appointment. After 3 attempts (or 4 attempts if we are towards the end of the recruitment phase), the RC will mark the participant as inactive and then mark the participant as “discontinued” if a new candidate is enrolled in the previous participant’s place.
 
If there is enough time and the participant has a mobile device, the RC will walk the participant through how to download GogyUp and create an account on their device or access GogyUp’s webapp.
	
Scripts:
 
 
• Baseline Assessment (Phone or Online Meeting)
 
• SMS Script – 1 Day Reminder
 
• Voice-mail – Missed Appointment
 
• SMS Script – Missed Appointment
 
 
Online Health Literacy Questionnaire (HLQ)
 
Online Demographic Questionnaire
				
7	
Provisioning
 
RC will enroll the participant in the assigned group.
 
An administrative assistant will send out:
 
  
 Intervention	Control	
   
  
 
• Directions for downloading the mobile app or accessing the webapp.
 
• Directions for creating a GogyUp account and signing into the study’s walled library.
 
• Enrollment Notice to Provider
 
 	 
 
• Packet of reading materials sent weekly
 
• Enrollment Notice to Provider
 
 	
  
 
RC will be provided daily activity reports by the administrative assistant. If a participant’s account has no activity at the start of the study period, the RC will contact the participant to ensure they have access to GogyUp and are able to log in.
	Intervention	Control	
 
• Directions for downloading the mobile app or accessing the webapp.
 
• Directions for creating a GogyUp account and signing into the study’s walled library.
 
• Enrollment Notice to Provider
 
	
 
• Packet of reading materials sent weekly
 
• Enrollment Notice to Provider
 
	
Scripts:
 
 
• Shipment Notification SMS / eMail
 
• Enrollment Notice to Provider
 

Intervention	Control					

 
• Directions for downloading the mobile app or accessing the webapp.
 
• Directions for creating a GogyUp account and signing into the study’s walled library.
 
• Enrollment Notice to Provider
 
	
 
• Packet of reading materials sent weekly
 
• Enrollment Notice to Provider
 
					

Step	Description	Documents & Scripts
8	
Follow-Up Assessment
 
RC conducts the follow-up assessment (remotely via phone or video call) of the HLQ.
 
The script for this step includes procedures for if the participant misses the appointment. After 3 attempts (or 4 attempts towards the end of the recruitment phase), the RC will mark the participant as “lost to follow up”.
 
If the participant was supplied with a GogyUp tablet supplied, the RC will ask if the participant would prefer to hold on to the tablet instead of a gift card.
 
.
	
Scripts:
 
 
• Follow-Up Assessment (Phone or Online Meeting)
 
• SMS Script – 1 Day Reminder
 
• Voice-mail – Missed Appointment
 
• SMS Script – Missed Appointment
 
 
Health Literacy Questionnaire (HLQ)

9	
Thank You Procedure and Notices
 
The RC will send participants who completed the Follow-Up Assessment and Follow-Up Appointment thank you note that either contains a \$25 gift card to reimburse network expenses / thank you for participating (if control group) or a notice that the tablet is now unlocked as may be used by the participant for their personal use.
	
Scripts:
 
 
• Thank You Note
 

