# RCT of Assistive-Reading Technology for Post-Visit Type 2 Diabetes Patient Education

Version 1.4

Protocol 1

10 February 2023

Due to rolling recruitment, the full study is expected to take up to 12 months, although if recruitment is faster than expected, the overall study may take less time.

Randomization is detailed below. In brief, we will randomize participants 1:1 at the individual level at enrollment using pre-generated trial allocation sequence from the National Cancer Institute's Clinical Trial Randomization Tool service (<https://ctrandomization.cancer.gov/tool/>) at recruitment. Study staff not involved in analysis will refer to an externally generated allocation sequence for intervention or comparison allocation. To avoid or limit randomization errors, the crosswalk file and the binary indicator for allocation arm will be known /available to study staff but not investigators involved in analysis or interpretation (until analyses are complete).

This study will include multiple primary care clinic sites in the sense that recruitment will occur at a health-system level in collaboration with Fairview research/trial support and therefore eligible patients can come from many clinics. However, recruitment, consent, pre-screening, data collection, and trial intervention itself are all remote— they do not occur in a clinical site.

Our planned analyses, also discussed in section 9, include an interim analysis approximately five to six months after the beginning of recruitment and data collection to provide preliminary data and feasibility/design information for a later Phase II SBIR application to NIH. This analysis will include all planned endpoints.

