### 7.3 MEASURES TO MINIMIZE BIAS: RANDOMIZATION AND BLINDING

We will use a random allocation sequence from the National Cancer Institute's Clinical Trial Randomization Tool (<https://ctrandomization.cancer.gov/tool/>). Study staff will refer to the allocation sequence to determine allocation arm for each newly recruited participant.. As such, study staff not involved in analysis will not be blinded because they will provide initial access to the GogyUp Reader app. Lastly, using an encrypted Microsoft Excel file for which only study staff not involved in analysis will have the password, study staff will create and enter the study id and trial arm into two crosswalk files: the first, a crosswalk identifying study id number with study arm (for unblinding following blinded analysis), and a crosswalk file linking intervention-arm study identification numbers to a separate id number from GogyUp internal data (for assessments of adherence; see above). Study staff will then enter name, contact information, study id and baseline variables into REDCap. Investigators (Drs. [name], [name], and [name] and [name]) will be blinded to participants' status, only have access to the REDCap file prior to analysis, and indeed will not have contact with participants. To support interim analysis, all procedures above will be followed, but for participants recruited during the first three months, an additional study id variable (interim study id) and REDCap trial arm indicator (interim indicator) will be used— these will ensure that the interim analysis (see above) does not effectively unblind the full analysis. After *interim* analysis, study staff will use the encrypted file to inform the investigators which random study arm number indicated which study arm. After *final* analyses, study staff will provide the password for the encrypted crosswalk files to the investigators for unblinding. The criterion for unblinding will be that all participants have had a final follow-up visit and (masked/blinded) comparative analyses are complete. In the unlikely event of an *unplanned* unblinding/breaking of randomization indicators, because investigators have no contact with participants and this protocol will be registered publicly, instigators will simply report the unplanned breaking and reasons for it in all subsequent publications for transparency.

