### 9.1 ENDPOINT AND OTHER NON-SAFETY ASSESSMENTS

Assessments for this study will include eligibility assessment and initial contact for pre-screening, as well as baseline and follow-up measures. We will also extract internal app data for the study period to assess adherence in the intervention arm (and to ensure no contamination in the control arm).

To ensure a focus on equitable representation and on a sample reflective of our interest in low income (publicly or non-insured) patients, the study team and health system research support staff determined that initial contact with recruiting materials (see above) will be prioritized to individuals seen at primary care clinics in the health system that see the largest proportions of publicly insured or non-insured patients. Iterative mailings will continue to prioritize patients from these clinics as well as patients in historically excluded and underrepresented groups (e.g., Black or Indigenous patients) among those fitting initial eligibility criteria (see above). Health system staff will conduct pre-screening procedures including identifying a potential sample and sending recruitment mailings (see Recruitment Collateral below). To ensure candidates are fully opted-in, GogyUp and study staff will not have access to any potential participants until participants contact GogyUp by filling out an online intake form or calling, texting, or emailing the GogyUp Research Coordinator through a study-designated phone number and email address listed on the recruitment letter.

Once eligible participants are consented by the GogyUp Research Coordinator, enrollment and baseline assessments will take place within an expected two-week (maximum) timeframe. Baseline assessments will include study staff administration (remotely via phone or video call) of the validated Health Literacy Questionnaire subscales 9 and 2, "Understanding health information" and "Having sufficient information," as well as the secondary outcome of the PDSMS. At three months post-baseline, study staff will conduct follow-up administration of the same outcomes. Based on our theoretical mechanism of action (see above), health literacy is the primary set of

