#### 15.4.2.5 COMPREHENSION CONFIRMATION INTERVIEW

*To be sure you understand what it means to participate in the study, I need to ask you a few questions.*

Open-ended questions to use:

1. “Describe in your own words the purpose of the study.”
2. “How would you explain to others what you will have to do in the study?”
3. “What is the possible benefit to you if you participate in this study? What are the possible risks?”
4. “How long does your participation in this study last?”
5. “Who do you contact if you have questions?”

Based upon the candidate’s responses, decide whether the candidate adequately understands the study.

---

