##### 15.5.1.1 STEP 5A: ASSIGNMENT & NEXT STEPS

Thank the participant for enrolling in the study and explain the assignment process.

Review procedure detailed in section 6.3 of the study protocol to assign participant to a study arm: intervention or control.

*I am going to unseal this envelop that contains your assignment.*

Unseal the envelope and show the card to the camera so that the participant may view the assignment.

---

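### No allocation concealment is specified: the role that judges comprehension and takes consent also looks up the arm in a pre-generated sequence, and the enrolment script describes a different, unreconciled envelope step

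*Combined protocol and SAP*

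**What the plan says.** **Who enrols.** Section 9.1 gives consent to the sponsor's research coordinator: "Once eligible participants are consented by the GogyUp Research Coordinator, enrollment and baseline assessments will take place". Before signature the coordinator asks open-ended questions and must "decide whether the candidate adequately understands the study" (15.4.2.5). Under 15.4.2.6 the coordinator can record a candidate as not ready. One contact can cover everything from intake to provisioning: "If the candidate chooses to proceed, the call may continue to Step 4, 5, 6, and 7" (11.1.4, Steps 3c and 3d).

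**Who assigns, and how.**
- Section 5.1.3: 1:1 individual randomization "using pre-generated trial allocation sequence from the National Cancer Institute's Clinical Trial Randomization Tool service". Staff outside the analysis consult it, and the arm indicator is open to study staff.
- Section 7.3: "Study staff will refer to the allocation sequence to determine allocation arm for each newly recruited participant".
- Section 11.1.4, Step 5, after the consent signature: "The research coordinator then refers to the allocation sequence to determine intervention or comparison arm for the newly recruited participant".
- Section 15.5.1.1, the script for the same step: "I am going to unseal this envelop that contains your assignment". The card is then shown to the camera. For the procedure the script points to section 6.3, which in this version is Lifestyle Considerations. Randomization is in 7.3.

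**Safeguards stated.** Sections 5.1.3 and 7.3 keep enrolling and assessing staff out of the analysis, keep the arm crosswalk from the analysing investigators, and defer unblinding until the masked analysis is done.

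**The concern.** Randomization protects the comparison only if the person who decides on entry cannot know which arm comes next. Here that decision includes a subjective judgement of comprehension, which lies close to the health-literacy outcome. It is made by coordinators of the company that developed the app. If upcoming rows can be seen, candidates could be moved forward or held back according to the next arm, knowingly or not.

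The planned ANCOVA (10.4.2) adjusts for the baseline score. It removes only the part of any selection that this score captures. The baseline itself may be taken after the arm has been announced (11.1.4, Step 5; 15.5.1.4), so it is not guaranteed to be free of arm knowledge. No later analysis can restore concealment. At stake is the reason that section 5.1.3 gives for randomizing at all, which is control of confounding.

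**Working it through.** **1. Order of events.** Put together, 11.1.4 and section 15 run: comprehension interview, signature, contact check, arm lookup, then baseline at once or at a later appointment. For a given participant the lookup follows the signature. A pre-generated list, however, holds the rows for later participants too. Someone who opens it for one participant can see the next row before interviewing the next candidate, unless something hides it.

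**2. Is anything said to hide it?**

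| Place | Mechanism | Concealment feature stated |
|---|---|---|
| 5.1.3 | Staff consult an externally generated sequence | None; arm indicator available to staff |
| 7.3 | Staff consult the sequence | None; the password protects the crosswalk files from investigators, not from staff |
| 11.1.4, Step 5 | Coordinator consults the sequence | None |
| 15.5.1.1 | Coordinator unseals an envelope on camera | Seal only; nothing on who prepares envelopes, opacity, numbering or link to the sequence |

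External generation makes the sequence random. It does not hide it from those who use it. Analyst blinding acts after enrolment and cannot undo selection at entry.

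**3. Do the two descriptions agree?** Envelopes could be filled from the generated sequence, so the descriptions can in principle be combined. No section does so, and the cross-reference that should link them leads to the wrong section. A coordinator cannot tell which governs.

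**4. Arithmetic: the plan's own figures first.** Section 10.2 gives an SD of 0.74 for subscale 9; the tests are two-sided at 5% (10.4.1).
- 80 per arm, difference 0.3: SE = 0.74 × √(2/80) = 0.117; 0.3/0.117 = 2.56; power ≈ Φ(2.56 − 1.96) = 73%, as stated.
- 60 per arm, difference 0.37: SE = 0.74 × √(2/60) = 0.135; 0.37/0.135 = 2.74; power ≈ Φ(2.74 − 1.96) = 78%, as stated.

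Concealment changes neither figure.

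**5. Illustration (assumed inputs).** The documents give no measure of selection. Let *b* be a prognostic difference between arms, in SD units of the analysed outcome, that remains after baseline adjustment. With no true effect, the test statistic is centred at *b* × √(n/2), and the rejection rate is P(|Z + *b*√(n/2)| > 1.96). For *b* = 0.1 and n = 80 the shift is 0.1 × √40 = 0.63, which gives about 10%. The t-test version gives:

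| *b* (SD) | 60 per arm | 80 per arm |
|---|---|---|
| 0 | 5% | 5% |
| 0.1 | 8% | 10% |
| 0.2 | 19% | 24% |
| 0.3 | 37% | 47% |

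Taking the SD as 0.74, 0.1 SD is 0.1 × 0.74 = 0.074 points, or 0.074/0.3 = 25% of the difference considered at 80 per arm. The bias could favour either arm.

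**The case against.** The strongest reply has four parts.

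*The lookup comes after consent.* This is correct. A reader might infer that the coordinator holds the list and knows the arm while judging comprehension. No section says so: Step 5 places the lookup after signature, and 7.3 ties it to each person already recruited. What stands is narrower: nothing in the plan prevents such foreknowledge.

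*The envelopes conceal, and they do not contradict the sequence.* A reader might call the two mechanisms incompatible. That goes too far, since envelopes can be made from a sequence, and an envelope opened on camera after consent could be a sound concealment step. Its preparation is not described, however, and three other sections describe a plain lookup.

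*The coordinator's power is limited.* Partly right. Section 7.3 speaks of study staff; only Step 5 names the coordinator. The schedule of activities and section 6.5 speak of coordinators in the plural, so this is one role and not necessarily one person. Rescheduling is offered as the candidate's choice. Access to a device is a weak route for selection, because the script in 15.5.1.3 asks about it only after assignment to the app arm. The comprehension judgement and the not-ready status remain with the coordinator, and nothing separates consenting from assigning.

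*It is a pilot, and staff are kept out of the analysis.* That separation protects the analysis, not enrolment. The results are meant to inform a larger trial (3.1, 5.1.3), so a biased estimate would be carried forward.

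**Conclusion.** The point holds as a gap in specification that goes beyond missing detail. Followed as written, 5.1.3, 7.3 and Step 5 give the enrolling role a pre-generated list with no stated barrier to reading ahead. Section 15.5.1.1 describes another step that is neither specified nor reconciled with them. The documents do not show that any coordinator has known an upcoming arm or that any selection has occurred.

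The size of a resulting bias is unknown. The rates of about 10%, 24% and 47% at 80 per arm (8%, 19% and 37% at 60) rest entirely on assumed residual imbalances of 0.1, 0.2 and 0.3 SD. They show what the test would do under such imbalances, not what is expected. The case for repair does not depend on them: the protection is standard, it is cheap here, and it cannot be added at the analysis stage.

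**What to change.** State one concealed mechanism, in the same terms, in 5.1.3, 7.3, 11.1.4 Step 5 and 15.5.1.1:

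- Existing staff who neither consent nor assess hold the sequence from the NCI tool. They keep it either as a REDCap list hidden from coordinators or as sequentially numbered, opaque, sealed envelopes that they prepare. REDCap is already in use, and an administrative assistant is already part of the workflow.
- Each assignment is released singly, only after the consent signature is locked and preferably after the baseline assessment is entered.
- Delete the text that has the coordinator refer to the sequence. In 5.1.3, limit staff access to arms already released.
- Correct the reference to 6.3 in 15.5.1.1 to 7.3.
- If baseline is placed before assignment, reorder the schema (2.2), Steps 5 and 6 of 11.1.4, and 15.5.1.4 to match.

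The cost is protocol wording, access rights or envelope preparation, and a small administrative step at each enrolment. If baseline comes first, assignment waits until it is complete, so a single call may not always reach provisioning. No participants or data are added.
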